TEXT MESSAGE INTERVENTION FOR ALCOHOL USE AND SEXUAL VIOLENCE IN COLLEGE STUDENTS

NCT05065918

JUNE 29, 2023

STATISTICAL DESIGN AND POWER

Aim 3: Conduct a pilot randomized trial to assess the full trial protocol and to generate estimates of multi-target intervention efficacy compared to an alcohol use reduction TM intervention. This aim will also explore gender and SV exposure as potential moderators of the intervention's effects.

Exploratory Hypotheses: The multi-target intervention will result in: a) greater decrease in alcohol use, and b) greater increase in the use of SV harm reduction behaviors, when compared to the alcohol use reduction condition

Primary Outcomes:

- 1) number of drinking days per month,
- 2) number of binge drinking days per month,
- 3) use of SV harm reduction strategies,

Secondary (Intermediate) Outcomes:

- 4) knowledge of SV harm reduction behaviors,
- 5) self-efficacy to use SV harm reduction behaviors

Analysis: Assessment of the full trial protocol will be conducted using descriptive statistics, including proportion of those recruited who are willing to be randomized, proportion adherence to the intervention and control treatments, and proportion who are retained three months post-intervention. These estimates will be crucial to design and success of a larger R01-scale study. In addition to descriptively assessing the full RCT protocol, we will conduct analyses of the specified exploratory outcomes, which serve as the basis for the full-scale study. Each exploratory outcome: 1) number of drinking days per month, 2) number of binge drinking days per month, 3) use of SV harm reduction strategies, 4) knowledge of sexual violence and alcohol risk, 5) self-efficacy to obtain sexual consent, and, will be tested for differences between the intervention and control conditions at T2 and T3 using generalized linear modeling. All models will be adjusted for age, SV history, and gender. Imbalances between groups on additional baseline characteristics (e.g., relationship status, residence, other substance use) will be assessed, and if differences are noted, variables will be included in multivariable models. Following intention-to-treat principles, analyses will be conducted on all who were randomized to a condition regardless of degree to which they interacted with the intervention. The estimates found in these analyses, including baseline prevalence estimates, will be used as the basis for sample size considerations in a larger R01-scale study. To assess the impact of missing data, we will compare the primary models (maximum likelihood) to full information maximum likelihood models; differences in results between the two models will be described. Participation biases and attrition analyses will be completed to inform future study design. The effect sizes calculated from these data will be used to estimate sample size needed for each outcome at $\beta = 0.2$ and two-sided $\alpha = 0.05$ for subsequent study.

Sample size considerations: Assessing 70 students per arm (total n=140) that have completed the program and follow up would provide sufficient data on the full RCT protocol across multiple campuses as well as estimates of intervention effects. Assuming a conservative retention rate of 70% for the three-month post-intervention follow up, we would need to enroll 200 participants at baseline. While we do not anticipate having sufficient power to detect statistically and clinically significant results, we have provided preliminary sample size calculations for our outcomes of interest. We estimated within-subject correlations to be between 0.2 and 0.6 between baseline and follow-up assessments.

Alcohol use (Number of drinking days, number of binge drinking days): Assuming a within-person correlation of 0.4 in alcohol use between baseline and follow up assessment, analyzing 70 students per arm (total n=140) would provide 80% power at $\alpha=0.05$ to detect a standardized difference of 0.395 between intervention and control. This translates to a 2-day greater reduction (SD=5.1 days) in number of drinking days in the past 30 days compared to a reduction seen with the control arm program. Given initials results of the control arm program, this would bring the total change needed to 3 fewer drinking days in the past 30 days from baseline

(150% greater efficacy compared to control program messaging). Assuming a 1-day greater decrease is possible with this intervention (2 days overall), 410 participants would need to be enrolled per arm (820 total), given 30% attrition.

SV Harm Reduction Strategy Use: Estimating a baseline prevalence of using at least one strategy at 25%, We believe a meaningful increase in any use is 30%. To achieve 80% power at an $\alpha=0.05$, and assuming a within-subject correlation of 0.4 between baseline and follow-up assessment, we would need 876 participants in each arm at follow-up; with 30% attrition, we would need to enroll over 2,500 total participants, at baseline. This sample sizes, however, are beyond the scope of the project. We believe enrolling 200 at baseline is feasible, providing 80% power at $\alpha=0.05$ to detect a 75% increase in any use of SV harm reduction strategies after accounting for attrition.

References

2. Strauss A. *Qualitative Analysis for Social Scientists*. New York: Cambridge University Press; 1987.

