Text Message Intervention for Alcohol Use and Sexual Violence in College Students

NCT05065918

June 29, 2023

Study Protocol

A randomized control trial to assess the full trial protocol and to generate estimates of multi-target intervention efficacy compared to an alcohol use reduction TM intervention. This aim will also explore gender and SV exposure as potential moderators of the intervention's effects.

Scientific Premise: Data from Aim 2 student participants will be used to systematically review message content and decision trees by the mentorship team and SAG. Study procedures will also be reviewed and revised using data obtained from campus faculty/staff during Aim 2. The pilot randomized trial will examine the potential efficacy of the multi-target TM-delivered intervention among college students seeking care from campus health centers. We will also begin to explore two hypotheses, that the multi-target intervention will show: 1) greater decrease in alcohol use than the alcohol use reduction condition and 2) greater increase in the use of SV harm reduction behaviors than the alcohol use reduction control condition. Intermediate outcomes of SV harm reduction behavior knowledge and self-efficacy will also be assessed. Exploratory analysis will be conducted to examine potential moderation effects of gender and SV history on the intervention's effectiveness. To achieve this aim, we will recruit 200 students from campus health centers. Findings from this aim will inform an R01-scale RCT of the multi-target TM intervention. Following intervention completion, a sub-group of participants will be invited to participate in semi-structured interviews to elicit feedback on their experiences participating in the intervention.

Setting: This phase of the intervention will continue to build on existing relationships from [name] campus health center work (See stakeholder letter of support). Student recruitment, eligibility requirements, screening and consent procedures will be as described in Aim 2 (the addition of recruitment sites will be used, as needed, to achieve the proposed sample size). Eligible students will complete baseline measures and be randomized via computer to the intervention (multi-target SV/alcohol use messaging) or control (alcohol use reduction messaging alone) condition. To examine potential moderators of intervention effect, stratified randomization will be used to ensure an equal distribution of students by gender and SV history.

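### The planned models do not name the baseline value of the outcome as a covariate, which gives up modest precision for the alcohol outcomes

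*SAP*

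**What the plan says.** The Analysis sections of both documents compare the arms on five outcomes at T2 and at T3 with generalized linear models. Both give the same fixed covariate set: "All models will be adjusted for age, SV history, and gender". Other covariates are conditional. Imbalances on further baseline characteristics "will be assessed, and if differences are noted, variables will be included in multivariable models". The examples attached to that rule are relationship status, residence and other substance use. No baseline outcome is among them, and no criterion for a difference is given.

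Other parts of the documents bear on this:

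- SAP, Exploratory Hypotheses: the first hypothesis is a "greater decrease in alcohol use".
- Protocol, Setting: "Eligible students will complete baseline measures and be randomized via computer".
- SAP, Sample size considerations: "We estimated within-subject correlations to be between 0.2 and 0.6 between baseline and follow-up assessments". For drinking days and binge days: "Assuming a within-person correlation of 0.4 in alcohol use between baseline and follow up assessment".
- SAP, Analysis, on missing data: "To assess the impact of missing data, we will compare the primary models (maximum likelihood) to full information maximum likelihood models".
- SAP, Analysis, on the use of the results: "The effect sizes calculated from these data will be used to estimate sample size needed for each outcome".

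**The concern.** The SAP treats baseline drinking as prognostic when it sizes the trial, then leaves it out of the models it specifies. Baseline drinking is the one prognostic variable whose strength the SAP quantifies. As written, it enters a primary model only if someone counts it as a further characteristic and judges the arms to differ on it.

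Two things are at stake. The first is precision: the pilot's effect estimates are meant to set the size of the R01-scale trial, so interval width matters even though the pilot does not claim adequate power. The second depends on dropout. The plan allows for 30% attrition. If dropout depends on baseline drinking, and its rate or its dependence on drinking differs by arm, a comparison of completers without baseline can be biased. With complete follow-up, leaving baseline out neither biases the estimate nor inflates type I error.

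**Working it through.** **Inputs.** From the SAP, Sample size considerations: 70 analysed per arm, SD 5.1 days, standardised difference 0.395, 80% power, α = 0.05, correlation r = 0.4, general range 0.2 to 0.6. Assumed: a two-sided test (stated only for the later study), a normal approximation, and age, SV history and gender explaining no outcome variance.

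**The plan's own figure.** Detectable difference = (1.96 + 0.8416) × √(2f/70), where f is the variance factor.

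- f = (1 + 0.4)/2 = 0.70, the mean of two correlated measures: 0.396, with 79.8% power at 0.395. This reproduces the SAP.
- f = 1 − 0.4² = 0.84, baseline as covariate: 0.434, power 72.2%.
- f = 1, follow-up only: 0.474, power 64.7%.

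The 0.70 factor is a separate sizing question. Adding baseline does not by itself restore 80% power at 0.395, and that gap is not counted here.

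**Cost of omitting baseline at one time point.** f = 1 − r². Power = Φ(0.395/√(2f/70) − 1.96). Half-width = 1.96 × 5.1 × √(2f/70).

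| Model | f | 95% CI half-width (days) | Power at 0.395 |
|---|---|---|---|
| Baseline omitted | 1.00 | 1.69 | 64.7% |
| Baseline in, r = 0.2 | 0.96 | 1.66 | 66.5% |
| Baseline in, r = 0.4 | 0.84 | 1.55 | 72.2% |
| Baseline in, r = 0.6 | 0.64 | 1.35 | 83.2% |

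At r = 0.4 an unadjusted analysis needs 70/0.84 ≈ 83 per arm to match an adjusted one with 70. Simulated 0 to 30 day counts (beta-binomial, assumed control means 6, 8 and 10, linear model, 4,000 replicates) agree: power 63–66% without baseline and 72–73% with it at r = 0.4.

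**Does the imbalance rule recover the loss?** Simulation: 60,000 replicates, 70 per arm, r = 0.4, normal data, t tests. Triggers are assumed, since none is stated.

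| Rule | Baseline enters | Power |
|---|---|---|
| Never | 0% | 64.3% |
| p < 0.05 | 4.9% | 64.9% |
| p < 0.10 | 9.8% | 65.3% |
| p < 0.20 | 19.8% | 66.1% |
| Std. difference > 0.25 | 14% | 65.6% |
| Std. difference > 0.2 | 24% | 66.4% |
| Std. difference > 0.1 | 55% | 68.7% |
| Always | 100% | 71.5% |

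The rule recovers between 64.9 − 64.3 = 0.6 and 68.7 − 64.3 = 4.4 of 71.5 − 64.3 = 7.2 points. Type I error was 5.1% for never and always, and 4.3% to 4.7% under the rule.

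**Dropout (illustrative).** 100 per arm, true effect −1 day, 20,000 replicates, assumed logit slope of dropout 1.0 per SD of baseline.

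- Attrition 40% control, 20% intervention: the unadjusted estimate shifts by +0.32 days at r = 0.4 (0.17 to 0.49 over r = 0.2 to 0.6). Reversed rates give −0.33.
- 35% versus 25%: +0.17. Slope 0.5 at 40% versus 20%: +0.19.
- Equal 30% attrition with slopes 1.0 versus 0: +0.52.
- Equal rates and equal slopes: 0.00.

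The adjusted estimate was off by less than 0.02 days in every setting.

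**If the later trial kept the same model.** For a 1-day difference at 80% power, n = 2f × 7.849 × 5.1² per arm at follow-up: 409 without baseline, 343 with it at r = 0.4 (392 at 0.2, 262 at 0.6).

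**Binary outcome.** Assume 25% any use at baseline and in control at follow-up, and 43.75% on intervention (the SAP's 75% increase). The marginal odds ratio is (0.4375/0.5625)/(0.25/0.75) = 2.33. Conditional on baseline, with baseline to follow-up correlation 0.2, 0.4 or 0.6, it is 2.43, 2.75 or 3.60. Reading the conditional value as marginal, with n = 7.849 × [p₁(1−p₁) + p₂(1−p₂)]/(p₂−p₁)², gives 88, 66 or 39 per arm instead of 97.

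**The case against.** The strongest reply is that this is an exploratory pilot that says it does not expect adequate power. At the plan's own correlation the half-width narrows by only 0.14 days, or 8%, and at r = 0.2 by only 0.03 days. This stands, and it is why the loss is called modest.

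The imbalance rule is open-ended, so baseline drinking is not excluded from it. Judged by the sampling SD of the estimate rather than by power, the rule does better: about 26%, 42% and 62% of the gap is recovered for p < 0.05, 0.10 and 0.20, and 51%, 68% and 94% for standardised differences above 0.25, 0.2 and 0.1. Mean interval width recovers less, about 4% to 53%. All of this depends on a trigger that the plan does not state.

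The talk of decrease, and of a baseline to follow-up correlation, may reflect an intended longitudinal model that was poorly described. If so, the defect is one of specification and the precision loss may be nil. But no such model is named, and the full information maximum likelihood comparison is not said to include baseline.

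The dropout rates and slopes are assumed, and attrition analyses are already planned. The near-zero adjusted bias follows from letting dropout depend only on baseline and arm. The later-trial sizes depend on the model that trial chooses; since baseline is collected, it could be sized with adjustment in any case. Both sets of figures are illustrations. Finally, no log-link count model was run, and the gain shrinks if the listed covariates share variance with baseline drinking.

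**Conclusion.** The concern holds and should be fixed. For a single-time-point alcohol comparison with 70 per arm and r = 0.4, the models as written give up 16% of the variance, or 8.3% of the standard error (1 − √0.84), and about 7 to 8 points of power at 0.395. Over the SAP's range of correlation the variance loss runs from 4%, which is negligible, to 36%, which is more than modest. The figures rest on the SAP's own correlation and SD, a normal approximation, and listed covariates that explain nothing. The bias under dropout is conditional on differential, baseline-dependent attrition and is not a prediction. Knowledge and self-efficacy were not quantified, because the documents give no SD or outcome-specific correlation for them.

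**What to change.** In the Analysis section of both documents, replace the covariate sentence with: *Each model will adjust for the baseline value of that outcome (where measured at baseline), age, gender and SV history, whatever imbalance is observed.* For any binary outcome, such as any use of SV harm reduction strategies, add: *A marginal (standardised) effect will be reported*, so that a baseline-conditional odds ratio is not used to size the later trial.

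The cost is two sentences, one degree of freedom per model and a standardisation step for binary outcomes. No new data are needed for outcomes measured at baseline. The protocol refers to Aim 2 for its measures and that list is not in the supplied documents, so the sponsor should confirm that knowledge and self-efficacy are collected at baseline. The basis of the 80% power statement needs to be aligned with the analysis model separately.

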Analysis: Assessment of the full trial protocol will be conducted using descriptive statistics, including proportion of those recruited who are willing to be randomized, proportion adherent to the intervention and control treatments, and proportion who are retained three months post-intervention. These estimates will be crucial to design and success of a larger R01-scale study. In addition to descriptively assessing the full RCT protocol, we will conduct analyses of the specified exploratory outcomes, which serve as the basis for the full-scale study. Each exploratory outcome: 1) number of drinking days per month, 2) number of binge drinking days per month, 3) use of SV harm reduction strategies, 4) knowledge of sexual violence and alcohol risk, 5) self-efficacy to obtain sexual consent, and, will be tested for differences between the intervention and control conditions at T2 and T3 using generalized linear modeling. All models will be adjusted for age, SV history, and gender. Imbalances between groups on additional baseline characteristics (e.g., relationship status, residence, other substance use) will be assessed, and if differences are noted, variables will be included in multivariable models. Following intention-to-treat principles, analyses will be conducted on all who were randomized to a condition regardless of degree to which they interacted with the intervention. The estimates found in these analyses, including baseline prevalence estimates and confidence intervals, will be used as the basis for sample size considerations in a larger R01-scale study. Due to the small sample size of this pilot study, we do not expect to be powered at α of 0.05, and will thus consider interactions terms at $p < 0.2$ worth exploring in stratified analyses. To assess the impact of missing data, we will compare the primary models (maximum likelihood) to full information maximum likelihood models; differences in results between the two models will be described. Participation biases and attrition analyses will be completed to inform future study design. The

effect sizes calculated from these data will be used to estimate sample size needed for each outcome at of 0.2 and two-sided α of 0.05 for subsequent study.

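### Extra covariates are chosen by chance baseline imbalance instead of prognostic value, with no criterion and no closed list; precision may be lost and the fitted model depends on judgement

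*SAP*

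**What the plan says.** Both documents settle three adjustment variables in advance: "All models will be adjusted for age, SV history, and gender" (SAP, Analysis). Two of them, gender and SV history, are also the randomisation strata: "stratified randomization will be used to ensure an equal distribution of students by gender and SV history" (Protocol, Setting).

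A second tier is conditional. The SAP refers to "Imbalances between groups on additional baseline characteristics (e.g., relationship status, residence, other substance use") and says that these imbalances "will be assessed, and if differences are noted, variables will be included in multivariable models". The Protocol's Analysis section carries the same sentence: "if differences are noted, variables will be included in multivariable models".

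The variables are given only as examples. Neither document says what counts as a difference (a p-value, a standardised difference or clinical judgement), who decides, or when. The baseline value of the outcome is not among the listed adjusters. The resulting effect sizes are to set the sample size of the follow-on trial.

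**The concern.** A covariate earns its place in a randomised comparison by predicting the outcome. Imbalance between arms at randomisation is chance, and carries no information on prediction. Under the stated rule a strong predictor is left out whenever the arms look alike, and an irrelevant variable comes in when they happen to differ. None of the three named variables is a stratification factor, so the design does not balance them.

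Two things are at stake. The first is precision that could be had from data already collected. The second is reproducibility: two analysts who follow the plan faithfully could fit different models and carry different effect sizes to the R01. For any use of an SV strategy under a logit link, the meaning of the odds ratio also shifts with the covariate set.

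**Working it through.** **Inputs from the documents.** 70 analysed per arm, 80% power, standardised difference 0.395, SD 5.1 days, within-person correlation 0.4 (SAP, Sample size considerations). Alpha is 0.05. I take it as two-sided, which is stated only for the follow-on trial ("two-sided $\alpha = 0.05$ for subsequent study").

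**Inputs assumed.** Three independent extra covariates; R², the share of outcome variance that they jointly explain beyond the fixed terms; and the criterion for a difference. The documents give none of these, so ranges are shown.

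**1. The plan's own figure.** The SAP says that "analyzing 70 students per arm (total n=140) would provide 80% power". With the variance multiplied by (1 + 0.4)/2 = 0.70:

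- 0.395 × √(70/(2 × 0.70)) = 2.793
- power = Φ(2.793 − 1.960) = 79.8%

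The 80% is reproduced, and the calculation does not use the extra covariates.

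**2. How often the rule brings a variable in.** For a p-value criterion the chance per variable is the threshold itself. For a standardised mean difference (SMD) above c, it is 2(1 − Φ(c/√(2/70))). The chance that at least one of three enters is 1 − (1 − q)³.

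| Criterion | Each variable (q) | At least one of three enters | At least one of three omitted |
|---|---|---|---|
| p<0.05 | 5% | 14% | >99.9% |
| p<0.2 | 20% | 49% | 99% |
| SMD above 0.2 in size | 24% | 56% | 99% |
| SMD above 0.1 in size | 55% | 91% | 83% |

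The undefined criterion alone moves the chance of any extra adjustment from 14% to 91%.

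**3. Cost to the standard error, p<0.05 criterion.** Unadjusted, SE = 5.1 × √(2/70) = 0.862 days. Always adjusting multiplies this by about √(1 − R²). Simulated linear models at n=140, which allow for the lost degrees of freedom, give for R² = 0.1, 0.2, 0.3:

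- mean reported SE under the rule: about 0.86 days throughout
- mean reported SE with fixed adjustment: about 0.83, 0.78, 0.73
- ratio: about 4%, 10%, 18% wider
- actual SD of the estimate under the rule: about 3%, 6 to 8%, 13% larger

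The last line is smaller because the rule does correct the worst imbalances while its reported SE takes no credit for that.

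**4. Lenient criterion, SMD above 0.1.** The SD of the estimate is 0.829, 0.779, 0.747 against 0.827, 0.779, 0.737 with fixed adjustment, so almost nothing is lost in the estimate. The reported SE is still about 2%, 5%, 9% too wide (at R² 0.2, 0.819 against 0.777).

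**5. Power on the SAP's own basis.** Replacing the factor 0.70 by 0.70 × (1 − R²), the 79.8% becomes 80.2%, 81.3%, 83.3%, 86.2% and 89.7% at R² = 0.01, 0.04, 0.09, 0.16 and 0.25 when the covariates are always included. Simulation at R² = 0.16 gives, for the rule against fixed adjustment:

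- 79.3% against 85.3% (p<0.05)
- 81.3% against 85.4% (p<0.2)
- 83.4% against 85.7% (SMD above 0.1)

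At R² = 0.01 simulation shows no gain once the lost degrees of freedom are counted.

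**6. Type I error.** Applied mechanically, with R² from 0.04 to 0.25, the rule gave 3.8% to 5.0%. It is slightly conservative, not inflated.

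**The case against.** The strongest reply is that the loss is conditional. It needs prognostic variables and a fairly strict criterion, and the documents supply neither. With a lenient criterion the estimate is nearly as precise as under fixed adjustment, and with weak predictors there is nothing to gain. Age and both stratification factors are always in the model. The study is an exploratory pilot that disclaims adequate power. All of this stands, and it limits the severity.

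The one predictor whose strength the SAP indicates is the baseline outcome: a correlation of 0.4, so about 0.4² = 16% of variance. Once it is in the model, increments of 10% to 30% from the three named variables are less plausible. That also stands, and the fix takes it in.

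For the binary SV-strategy outcome, the linear-model SE gains do not carry over to a logit coefficient. At 25% of 140 there are about 35 events, so a long list could overfit.

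Four stronger readings might be inferred, and the documents do not support them:

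- **The rule cuts power from 80% to about 65%.** An unadjusted test that ignores the 0.4 correlation gives Φ(0.395 × √35 − 1.960) = 64.7% with no covariate rule at all. That gap is not a cost of the rule.
- **The rule inflates false positives.** Taking the smallest p-value over all subsets of three covariates would give about 8% to 11% per test at R² 0.1 to 0.3. That ignores balance altogether, whereas the plan conditions on it.
- **Variables are chosen after outcomes are seen.** The timing is not stated, and balance can be checked before follow-up.
- **Every observed difference is chance.** This holds for all students as randomised. With 30% attrition, differences among those analysed need not be.

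**Conclusion.** The concern holds in a limited form. The rule selects covariates on imbalance and not on prognostic value, from an open list and without a criterion. If the named variables predict the outcome, precision is given up: under p<0.05 the reported SE is about 4% to 18% wider for an assumed joint R² of 0.1 to 0.3. Under an SMD criterion of 0.1 the cost is mainly a reported SE about 2% to 9% too wide, and near R² 0.01 there is no cost. These sizes rest on three independent covariates, 70 per arm and a linear model.

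Whatever the R², the choice of model depends on chance imbalance and analyst judgement. The effect size carried to the R01 can shift with that choice to the extent that the variables are prognostic. Severity is moderate to minor.

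**What to change.** Delete the imbalance sentence from the Analysis section of both documents. Before outcome data are seen, specify a closed covariate set for each outcome, used at T2 and T3 whatever the observed balance: age, gender, SV history, the baseline value of that outcome, and those of relationship status, residence and other substance use that are expected to predict it.

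Collapse sparse categories, and keep the set small for the binary SV-strategy outcome. Describe baseline characteristics by arm without significance tests. Report the model with only age, SV history and gender as a sensitivity analysis.

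The cost is one rewritten sentence in each document, a short list per outcome and a few degrees of freedom. It needs no new data, because the plan already intends to assess these baseline variables. If the added variables prove weakly prognostic, the gain in precision will be little or none, but the model will be reproducible.

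### The 80% power stated for 70 per arm does not belong to the analysis described: power is about 65% at each time point as listed, about 72% with the baseline outcome added

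*SAP*

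**What the plan says.** The SAP's Sample size considerations plan for 70 analysed students per arm and reach 200 enrolled by "Assuming a conservative retention rate of 70% for the three-month post-intervention follow up". They give a correlation range: "We estimated within-subject correlations to be between 0.2 and 0.6 between baseline and follow-up assessments".

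- **Alcohol use.** With a "within-person correlation of 0.4 in alcohol use between baseline and follow up assessment, analyzing 70 students per arm (total n=140) would provide 80% power" is claimed "to detect a standardized difference of 0.395 between intervention and control". This is put at 2 drinking days with an SD of 5.1, and "this would bring the total change needed to 3 fewer drinking days in the past 30 days from baseline". For a 1-day difference, "410 participants would need to be enrolled per arm (820 total), given 30% attrition".
- **SV harm reduction strategies.** Baseline use is taken as 25%. The SAP says "We believe a meaningful increase in any use is 30"%, and for that "we would need 876 participants in each arm at follow-up; with 30% attrition, we would need to enroll over 2,500 total participants". It adds that enrolling 200 gives 80% power for a 75% increase after attrition.

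The SAP's Analysis section, like the protocol's, tests each outcome between arms at T2 and T3 with generalized linear models adjusted for age, SV history and gender. Covariates that look imbalanced at baseline may be added. The baseline value of the outcome is not on the list. Neither document says whether T2 and T3 share one model or are averaged. Both say in general terms that sufficient power is not expected.

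**The concern.** A baseline-to-follow-up correlation can improve precision only if the analysis uses the baseline outcome, and the listed model does not. If the baseline outcome were used in the usual way, a correlation of 0.4 would give a smaller gain than the SAP's figures need. So the stated power appears to belong to some other, unnamed analysis.

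What is at stake is how the pilot's results are read. A reader of the SAP will take 2 drinking days, or a 75% rise in SV strategy use, as effects the study would miss one time in five. Under the listed model with 70 per arm the miss rate is about 35% at each time point, so a null result says less than the SAP implies. The 410 and 876 figures could also mislead planning of the later trial, but only if the same formula is reused, since the Analysis section re-estimates that trial's size from the pilot's effect sizes.

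**Working it through.** **Inputs from the SAP:** 70 analysed per arm; 0.395 SD; SD 5.1 days; correlation 0.4 (range 0.2–0.6); SV baseline use 25%; 30% attrition; alpha 0.05. **Assumptions:** two-sided testing (the SAP says so only for the later study), normal approximation, and no precision gain from age, SV history and gender.

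**Formulas.** Let f multiply the ordinary two-arm variance.

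- Detectable difference (in SD) = (1.960 + 0.842) × √(2f/70)
- Power at 0.395 SD ≈ Φ(0.395/√(2f/70) − 1.960)
- Analysed n per arm for 1 day = 2f × 2.802² × 5.1²; enrolled = analysed/0.70
- SV: n per arm from the pooled two-proportion formula, multiplied by f

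**Step 1: reproduce the SAP with f = 0.70.**

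| SAP figure | Calculation | Result |
|---|---|---|
| 0.395 SD | 2.802 × √(1.40/70) | 0.396 |
| 80% power, alcohol | at 0.395 SD | 79.8% |
| 410 enrolled per arm | 286/0.70 | 408 (409 if 286 is rounded up first) |
| 876 per arm | 25% vs 30%: 1,250.7 × 0.70 | 875.5 |
| 70 per arm, 75% SV rise | 25% vs 43.75%: 99.5 × 0.70 | 69.7 |

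All the figures share this factor, so rounding does not explain it.

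**Step 2: power for 0.395 SD at 70 per arm under each candidate analysis, with r = 0.4.**

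| Analysis | f | Power | Detectable at 80% |
|---|---|---|---|
| Listed model, one time point | 1.0 | 64.7% | 0.474 SD (2.4 days) |
| Baseline outcome as covariate | 1 − r² = 0.84 | 72.2% | 0.434 SD (2.2 days) |
| Change score | 2(1 − r) = 1.2 | 56.9% | 0.519 SD (2.6 days) |
| T2/T3 average | (1 + r)/2 = 0.70 | 79.8% | 0.396 SD (2.0 days) |
| T2/T3 average plus baseline outcome | 0.70 − 0.16 = 0.54 | 88.9% | 0.348 SD (1.8 days) |

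In the T2/T3 average row, r is the T2–T3 correlation; the last row takes r = 0.4 for every pair of measurements. Only the T2/T3 average matches the SAP. With a baseline covariate, f = 0.70 would need r of about 0.55; with a change score, about 0.65. Simulation of 20,000 normal-data trials agrees: 63.8% at one time point, 71.3% with the baseline covariate, 79.1% for the T2/T3 average.

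**Step 3: SV strategies.** Power for 25% vs 43.75% at 70 per arm is 80.2% with f = 0.70, 72.6% with 0.84 and 64.9% with 1.0. The corresponding detectable rates are 43.7%, 45.6% and 47.6%, which are relative rises of about 75%, 82% and 90%. For a binary outcome 1 − r² is an approximation. A logistic simulation gave 63.0% without and 70.6% with the baseline outcome.

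**Step 4: sensitivity for alcohol.**

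- *Correlation 0.2 to 0.6.* Power rises from 66.5% to 83.2% with a baseline covariate, but falls from 85.5% to 74.3% for a T2/T3 average. The contrast therefore decides which end of the SAP's range is favourable.
- *More students at T2.* The 70% retention is for the three-month follow-up, and none is given for T2. In the listed model, 70, 80, 90 and 100 per arm give 64.7%, 70.5%, 75.5% and 79.8%.
- *Counting a result at either time.* With equal effects, 70 per arm at both times and a T2–T3 correlation of 0.4, the chance of missing at both is 18.3% (15.3–21.6% over 0.2–0.6). The false-positive rate is then 9.3%. A Bonferroni split brings power for at least one time to 72.2%.
- *Count data.* Simulated counts capped at 30 days, with SD 5.1, about a 2-day difference and an assumed control mean of 6 to 12 days, give 64–67%.

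**Step 5: the SV 30%.** The 876 fits 25% rising to 30%. A 30% relative rise (25% to 32.5%) needs 570.5 per arm, or 399 after the factor. The 75% increase, by contrast, fits only as a relative rise (25% × 1.75 = 43.75%).

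**The case against.** The best defence is that the plan is under-specified rather than wrong. A joint model for T2 and T3 with a common within-person correlation of 0.4 gives exactly 0.70, and the SAP does not exclude such a model. Averaging and also adjusting for baseline gives 88.9%, so 80% lies inside the range of plausible readings. The 65% is also cautious: covariates explaining 10% of the variance (an assumption) would raise it to about 69%, more students may be seen at T2, and maximum likelihood on everyone randomized may use more than the completers. Finally, this is a pilot with exploratory outcomes, and both documents disclaim adequate power.

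Some of this stands. The 80% is not an arithmetic slip, and it would hold for a prespecified T2/T3 average. But the SAP labels its 0.4 as baseline to follow-up, names no pooled contrast and gives no T2–T3 correlation. The average-plus-baseline reading does not reproduce the stated figures either.

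The documents cannot show where 0.70 came from. It also equals the retention rate, so an unadjusted test on all 100 enrolled per arm gives the same 79.8% and 80.2%. That is not a test on 70 analysed. A one-sided test with the baseline covariate would give 81.7%, but nothing in the documents states one-sided testing. A general disclaimer does not correct a specific 80% figure. It does limit the consequences.

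**Conclusion.** The concern holds: the stated 80% is not the power of the analysis the SAP describes. With 70 analysed per arm, two-sided 0.05 and no gain from the listed covariates, power at each time point is about 65% for both 0.395 SD in alcohol use and a 75% relative rise in SV strategy use. Adding the baseline outcome at r = 0.4 gives about 72% for alcohol and roughly 71–73% for SV; 80% for alcohol is reached only if r is about 0.55 or more.

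This should be fixed but does not threaten the pilot. No planned analysis depends on the 80%. The harm is a misleading reference point for null results and, if the formula is carried forward, larger-trial figures that are too small for the listed model. The double meaning of the SV percentage increase is a lesser wording fault.

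**What to change.** Name one contrast, its covariates and the correlation used, and make the power figures follow from them.

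- **(a) Keep the listed model, per time point.** State about 65% power at the present effects, and 80% power for about 0.474 SD (2.4 days) or about a 90% relative SV rise. The larger-trial figures become about 584 enrolled per arm for 1 day (408.3/0.70) and about 1,251 per arm at follow-up for 25% vs 30%. Drop the 0.4, and say whether T2 or T3 is the main time point.
- **(b) Add the baseline outcome as a covariate at r = 0.4.** State about 72% power at 0.395 SD and 80% for about 0.434 SD (2.2 days), with about 490 enrolled per arm for 1 day. For SV, approximately an 82% relative rise, and 1,051 per arm for 25% vs 30%.
- **(c) Prespecify the T2/T3 average.** State 0.4 as the T2–T3 correlation. The 80% then stands, provided the effect is equal at both times and both are observed.

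Under any option, say whether the SV 30% means 25% rising to 30% or a relative rise (about 571 per arm at f = 1.0).

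The cost is SAP wording for (a), one covariate for (b) and one longitudinal contrast for (c). Enrolment is unchanged; under (a) and (b) the stated figures become less favourable.
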